Treatment groups will be dummy coded with CC (coping control) used as the reference group. We will test for treatment condition effects on the stress and symptom outcome measures using MLMs as we did in our publications in the R21 feasibility trial. MLMs provide an optimal analytic strategy because they model all available data (following intent-to-treat principles in RCTs) and allow us to flexibly evaluate the nested nature of this data structure. Specifically, we will create (for EMA) 3-level MLMs (levels: individual participants; day; within-day time) using restricted maximum likelihood estimation. The 3-level EMA MLMs testing each aim will compare the 3 treatment intervention groups on each dependent variable (e.g., daily stress) from the pre, post, and follow-up training measurement occasion. The 3-level models will include a random intercept for day nested within participant. Measurement occasion (pre, post intervention, follow-up), group condition, day-specific factors (e.g., day-of-week or weekday versus weekend), and within-day time will be modeled as fixed effects. All models will be fit with compound symmetric variance-covariance data structure but other structures (e.g., autoregressive covariance structure, ARH(1), spectral power) will be evaluated using Akaike's Information Criterion (AIC). We have specified this initial approach for modeling random and fixed effects, but we will evaluate whether this approach best fits the data using likelihood ratio tests and AIC. In testing each aim, each measurement occasion  $\times$  treatment interaction will be evaluated with a decision rule that a significant effect is observed when the measurement occasion  $\times$  treatment interaction statistic and corresponding p-value is less than .05 (two-tailed). When a significant interaction is observed, follow-up planned contrasts in each MLM will compare specific groups at post-training. To help with benchmarking we will provide effect size statistics corresponding to the magnitude of change over time, and between groups at each post-treatment time point. One strength of our approach here is that it extends an established MLM data analytic pipeline we used in our three-arm EMA R21 trial publications with success, along with MLM mediation analyses in other MBSR RCT publications.

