**Testing our Hypotheses.** We are specifying a priori predictions about the effects of MA-MBSR intervention, relative to MO-MBSR and CC. Thus no statistical corrections for multiple comparisons will be made for our primary study hypotheses or specified pair-wise comparisons. When additional exploratory analyses are conducted, a Holm's correction will be made for multiple comparisons. We have previously published our MLM approach evaluating MA-MBSR effects relative to these two control groups (see Chin et al., 2019 or Lindsay et al., 2018 publications)—so here we highlight our equations and approach. In previous work we have focused on stress, so below we apply this approach to evaluating hypothesis #2, specifying that MA-MBSR will reduce symptoms relative to MO-MBSR and CC. This hypothesis will be tested separately for clinician assessed, physician assessed or patient self-reported symptoms (using the IBS-SS). The general form of the model to be tested, exclusive of covariates, is as follows, in mixed model

notation:

IBS symptomsit =  $\gamma_{00} + \gamma_{01} \cdot (\text{txgroup}_i) + \gamma_{10} \cdot (\text{time}_{it}) + \gamma_{11} \cdot (\text{txgroup}_i) \cdot (\text{time}_{it}) + u_{0i} + e_{it}$  where IBS symptomsit is the composite symptoms score for individual  $i$  at time-point  $t$ , timeit is the measurement occasion (pre, post intervention, or follow-up) assessment time of year, txgroupi is the treatment group a participant is assigned to. In multilevel notation:

$$\begin{aligned} \text{Level 1: } & \text{Symptoms}_{it} = \beta_{0i} + \beta_{1i} \cdot (\text{time}_{it}) + e_{it} \\ \text{Level 2: } & \beta_{0i} = \gamma_{00} + \gamma_{01} \cdot (\text{txgroup}_i) + u_{0i} \\ & \beta_{1i} = \gamma_{10} + \gamma_{11} \cdot (\text{txgroup}_i) \end{aligned}$$

The primary test of hypothesis is the F-test of the null hypothesis  $H_0: \gamma_{11} = 0$ . Note that this general model will be used, with different outcomes (e.g., stress) and for subsequent aims below but will not be repeated.

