For hypothesis #3, we will use EMA-sampled IBS symptom severity to test whether EMA-sampled stress reduction will statistically mediate symptom improvements. We will test for concurrent relations between EMA-sampled stress and IBS symptom severity (within the same moment) and also test lagged relations (stress at time  $t$  predicting IBS symptom severity at time  $t+1$ ). To conduct this mediation analysis, we will compare two MLMs that use IBS symptom severity as the outcome and group condition as a fixed effect: one MLM will include stress as an additional fixed effect, and another will not. If the fixed effect for group condition is statistically significant in the latter but not the former, stress reduction will be declared to act as a mediator for symptom improvements.

For hypothesis testing, we will first run unadjusted models without covariates, as described above. Then, as a sensitivity analysis, we will run adjusted models that incorporate baseline characteristics related to sociodemographic covariates (sex, gender, age, race), clinical covariates (IBS subtype, baseline IBS symptom severity, baseline perceived stress), and other time-related covariates such as day-of-week when appropriate (e.g., for analyses involving EMA samples where we observe repeated measures across and within days).

**Attrition and Missing Data.** We expect minimal participant attrition (<15%) during the study period across conditions. Dropouts are not expected to be a function of the missing outcome data given the observed. Our unadjusted analyses assume data are missing completely at random, while our adjusted analyses loosen this assumption to allow for data to be missing at random. We will also assess the sensitivity of our results to violations of the missing-at-random assumption (e.g., via pattern-mixture models). Additionally, we will evaluate whether adherence to the program and EMA vary across groups. To evaluate attrition, we will compare study dropouts to study completers based on observed participant characteristics.

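### Hypothesis 3 infers mediation from the group effect losing significance once stress is added; that is not a test of the indirect effect and can miss real partial mediation.

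*SAP*

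**What the plan says.** Under Testing our Hypotheses, the SAP addresses hypothesis 3 (that EMA-sampled stress reduction mediates symptom improvement) by a plan to "compare two MLMs that use IBS symptom severity as the outcome and group condition as a fixed effect". Of these, "one MLM will include stress as an additional fixed effect, and another will not". Mediation is concluded if the group effect is "significant in the latter but not the former, stress reduction will be declared to act as a mediator for symptom improvements". The latter is the model without stress and the former the model with it.

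The SAP will "also test lagged relations" between stress and symptoms as well as concurrent ones, but neither enters the declaration. It plans no estimate, interval or test of the indirect effect.

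Three other statements bear on the point:
- Treatment effects on stress are modelled in their own right: "We will test for treatment condition effects on the stress and symptom outcome measures using MLMs".
- The group-by-occasion model carries over, since "this general model will be used, with different outcomes (e.g., stress) and for subsequent aims below".
- After a significant interaction, "follow-up planned contrasts in each MLM will compare specific groups at post-training".

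Which groups and which term are tested is therefore covered elsewhere and is not at issue here.

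**The concern.** The rule has two conditions. The first, a significant group effect on symptoms, is a conservative but defensible gate. The second, a non-significant group effect once stress is in the model, is the fault. A non-significant direct effect is not evidence of an indirect one, and a significant direct effect does not exclude one. The rule compares two significance verdicts; it tests neither the product a×b nor the change in the group coefficient.

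Hypothesis 3 speaks of mediation and does not specify full mediation. If stress reduction explains part of the benefit and another mechanism explains the rest, the hypothesis is true, but the rule becomes less and less able to say so as the remaining direct effect is estimated more precisely. Because the SAP offers no other criterion, the trial could fail to declare a real effect through stress. The tests of treatment on stress and on symptoms are unaffected.

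**Working it through.** **Inputs.** From the SAP: the two-model rule, three arms, and two-sided 0.05 (stated for the occasion-by-treatment interaction, assumed here for the group effect). It gives no sample size, effect size or SD, so there is no figure of its own to reproduce. All sizes below are assumptions.

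**Large-sample behaviour.** With c′ the direct effect, P(declare) ≤ P(direct effect not significant) ≈ P(|Z + c′/SE| < 1.96). If c′ ≠ 0, SE shrinks with n and this bound goes to zero, whatever the size of a×b.

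**Check by hand (two arms, one occasion).** Let M = aG + e₁ and Y = c′G + bM + e₂, with unit error SDs, a = b = 0.5 and c′ = 0.25, so the total effect is 0.25 + 0.25 = 0.50 and half is mediated.
- At 100 per arm, SE(total) = √[(2/100)(1 + 0.5²)] = 0.158; 0.50/0.158 = 3.16; power ≈ Φ(1.20) = 0.885.
- SE(direct) = √[(2/100)(1 + 0.5²/4)] = 0.146; 0.25/0.146 = 1.71; power ≈ Φ(−0.25) = 0.40.
- A significant direct effect nearly always comes with a significant total effect, so P(declare) ≈ 0.885 − 0.40 ≈ 0.48. Simulation (4,000 runs) gives 0.479. Testing paths a and b jointly gives 0.94.
- At 300 per arm, SE(direct) = √[(2/300)(1.0625)] = 0.084; 0.25/0.084 ≈ 2.97; power ≈ Φ(1.01) = 0.84. The total effect is then always significant, so P(declare) ≈ 1 − 0.84 = 0.16. Simulation gives 0.158, against 1.00 for the joint test.

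**Three arms, pre/post change.** MO-MBSR is set equal to CC, the change SD is 1, and there are 4,000 replicates per cell. The rule uses the 2-df group test. The comparator is a 95% Monte Carlo interval for a×b (MA-MBSR vs CC) that also requires a significant group effect on symptoms, so the difference isolates the second condition. Share mediated = ab/(ab + c′).

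| a, b, c′ | Share mediated | Rule at 50/100/150 per arm | Gated interval | Loss (points) |
|---|---|---|---|---|
| 0.5, 0.4, 0.5 | 0.20/0.70 = 29% | 23, 5, about 0.5% | 67, 95, 99% | 44, 90, about 98 |
| 0.5, 0.4, 0.2 | 0.20/0.40 = 50% | 30, 51, 54% | 36, 76, 91% | 6, 25, 37 |
| 0.7, 0.5, 0.15 | 0.35/0.50 = 70% | 53, 76, 76% | 61, 92, 99% | 8, 16, 23 |
| 0.5, 0.5, 0 | 100% | 17, 31, 48% | 17, 33, 51% | 0, 2, 3 |

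Repeat runs agree within simulation error; the smallest cell ranges from 0.3% to 0.6%. With half mediated the rule then falls to 32% at 300 per arm and 5% at 600; with 70% mediated, to 60% and 27%. So at realistic sizes the decline shows only when the direct effect is large relative to its standard error. Otherwise declarations first rise with n and fall later.

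**False declarations, no indirect path and no confounding.** With direct effect 0.5 and (a, b) = (0.8, 0), (0.5, 0) or (0, 0.5), the rule declares mediation in 0.1–8.5% of trials. The two-arm version with a = 0.8, b = 0 and c′ = 0.4 peaks at just under 10%.

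**Occasion-level confounding.** With b = 0 and a residual stress–symptom correlation of 0.2, the rule declares mediation in 20%, 13%, 4% of trials and the ungated interval in 46%, 89%, 98%. At correlation 0.4 the figures are 39%, 32%, 18% and 70%, 94%, 99%.

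**Secondary: one stress term.** The SAP does not state how stress is centred. In an assumed layout of 2 occasions × 3 days × 5 prompts, with a momentary slope of 0.4, no between-occasion slope, and only person and day intercepts ("The 3-level models will include a random intercept for day nested within participant"), the rule declares mediation in 21%, 12%, 5% of trials.

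**The case against.** The strongest objection concerns the replacement. Stress and symptoms are both self-reported by EMA, so shared occasion-level influences are plausible, and under such confounding an indirect-effect interval makes more false claims than the present rule. The figures above confirm this, and the objection stands as a real cost. It does not rescue the rule, which does better there only because it rarely declares anything once the direct effect is significant. That is not control of confounding. The planned adjusted models include baseline perceived stress and baseline symptom severity; these bear on stable differences between people, not on influences that vary by occasion.

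Four stronger readings are tempting, and the SAP does not support them.
- A reader might infer that the SAP would report stress as shown not to mediate. It says *if*, not *only if*, and does not say what is concluded when the rule fails. The fault is that no other criterion is given.
- A reader might infer that the rule commonly produces false mediation. Without confounding and without an indirect path its rate is modest. Rates of 39%, 43%, 34% for a purely momentary link arise only after adding a person-by-occasion intercept. The SAP does not name that term, though it leaves the random structure open to likelihood ratio tests and AIC.
- A reader might treat the missing centring as an equal fault. Nothing in the SAP shows that momentary and between-occasion slopes differ, so it is a secondary note.
- A reader might take the rule's 17% at 50 per arm under full mediation as damage from the second condition. The gated interval also gives 17%; the limit there is power for the total effect.

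**Conclusion.** The point holds and should be fixed. Losing significance is not a test of the indirect effect, and the eventual failure under partial mediation in the same direction follows from the rule itself, without any assumed sizes.

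How much is lost depends on assumptions the SAP cannot settle. The loss is very large when about 29% is mediated. With half or 70% mediated it is 6–8 points at 50 per arm and 23–37 points at 150. Under full mediation it is at most 3 points. The main figures come from a linear pre/post change model with MO-MBSR equal to CC and no confounding; the follow-up occasion was not simulated. Only the conclusion on hypothesis 3 is affected.

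**What to change.** In the hypothesis 3 paragraph:

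1. Delete the condition that the group effect be non-significant with stress in the model.
2. For MA-MBSR vs CC and MA-MBSR vs MO-MBSR, estimate a×b at post-training. Path a is the group-by-occasion effect on EMA stress. Path b is the within-person, between-occasion stress slope, from a symptom model with group, occasion and their interaction in which the person mean, the occasion deviation and the momentary deviation of stress are separate terms. Only the occasion term enters a×b.
3. Declare mediation if the 95% Monte Carlo or participant-level bootstrap interval for a×b excludes zero. If a significant occasion-by-treatment effect on symptoms is wanted first, state it as a gate.
4. Report the direct effect with its interval, and the lagged relation alongside as evidence on temporal order.
5. With any declaration, report a×b over a range of assumed occasion-level residual correlations (for example 0 to 0.4), with the value at which the interval first includes zero. Word the claim as conditional on no such confounding.

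Latent occasion means are an optional sensitivity analysis if prompts per occasion are few.

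The cost is SAP wording and analysis code: the three-term split, the interval and the sensitivity analysis. No new data are needed. Because the interval is more exposed to occasion-level confounding than the present rule, step 5 cannot be left out.

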## *Data Analysis Strategy.*

**Overview of Data Analyses.** Our study team specializes in statistical analysis and measurement models related to those described in this proposal. [name] and our team biostatistician (co-I [name]) will coordinate the data analytic aspects of the project, and carry out the proposed mixed effect linear models (MLMs). A secure de-identified database will be maintained by the PI and project coordinator (see Budget Justification). A CONSORT flowchart will be generated in Year 1 that tracks participants through the study. Descriptive statistics will be used to characterize the sample, and chi- square and one-way ANOVAs will be used to evaluate success of randomization on primary variables of interest. In addition to the MLMs presented below, as a sensitivity analysis we will also consider MLMs that adjust for baseline variables of interest. To help explain study attrition, chi-square and independent-sample t-tests will compare dropouts to non-dropouts. We are defining successful treatment completion as having completed 11 out of the 14 available lessons. While our primary analyses follow intention-to-treat principles, we will also assess how sensitive results are to excluding subjects who do not successfully complete their respective treatment.

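### The adjusted sensitivity model can put an outcome's pre score on both sides of the equation, and the unadjusted mixed model is wrongly said to need MCAR

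*SAP*

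**What the plan says.** In the SAP's Testing our Hypotheses section, the time variable in the symptom model "is the measurement occasion (pre, post intervention, or follow-up) assessment time of year", so the pre score is one of the responses. The same general form is reused for other outcomes, stress among them. On the symptom outcomes: "This hypothesis will be tested separately for clinician assessed, physician assessed or patient self-reported symptoms (using the IBS-SS").

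The Overview of Data Analyses announces that "as a sensitivity analysis we will also consider MLMs that adjust for baseline variables of interest". After the text on hypothesis 3, the adjusted models are described as including, among others, "clinical covariates (IBS subtype, baseline IBS symptom severity, baseline perceived stress"). No instrument is named for these covariates. Nothing removes the pre row from the response, and nothing leaves out a covariate that is the pre value of the outcome being modelled.

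The modelling paragraph starts every model from compound symmetry and adds that "other structures (e.g., autoregressive covariance structure, ARH(1), spectral power) will be evaluated using" AIC. It makes the occasion-by-treatment interaction the decision and the gate: "When a significant interaction is observed, follow-up planned contrasts in each MLM will compare specific groups at post-training".

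Under Attrition and Missing Data, the SAP first states: "Dropouts are not expected to be a function of the missing outcome data given the observed". It continues: "Our unadjusted analyses assume data are missing completely at random, while our adjusted analyses loosen this assumption" to MAR.

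**The concern.** There are two linked problems.

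1. If an outcome's pre score is both a response and a covariate, a single covariate slope has to describe the pre score regressed on itself (true slope 1) and the later scores regressed on the pre score (true slope r, the within-person correlation when variances are equal). It can fit neither. The adjusted model is there to show whether the primary result is robust, so its post-training contrasts should have correct standard errors.

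2. The MCAR sentence misdescribes the main analysis and ranks the two models on a wrong basis. If the planned comparison of dropouts with completers finds differences, a reader who takes the sentence literally would trust the unadjusted model less than it deserves. For an affected outcome, that reader would turn to the model with the first problem.

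**Working it through.** The SAP gives no sample size, variance or correlation, so there is no planned figure to reproduce. **Assumed throughout:** three occasions, unit variances, true compound-symmetric correlation r = 0.3, 0.5 or 0.7. The first two checks also assume complete data, and 60 per arm (N = 180) where a sample size is needed.

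**Compound symmetry retained.** With balanced data, the slope of a participant-level covariate is the slope of the participant's mean response on it.
- Common slope: b = (1 + r + r)/3 = (1 + 2r)/3.
- Residual variance at pre: (1 − b)².
- True residual variance at post or follow-up: 1 + b² − 2br.
- Variance the model uses at every occasion: the mean of the three.
- Standard error ratio (model over true): the square root of model variance over true post variance.
- Error of an ungated two-sided 5% post-training contrast: 2Φ(−1.96 × ratio).

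| r | b | pre variance | true post variance | model variance | SE ratio | error |
|---|---|---|---|---|---|---|
| 0.3 | 0.533 | 0.218 | 0.964 | 0.716 | 0.86 | 9.1% |
| 0.5 | 0.667 | 0.111 | 0.778 | 0.556 | 0.85 | 9.8% |
| 0.7 | 0.800 | 0.040 | 0.520 | 0.360 | 0.83 | 10.3% |

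For r = 0.5, the model variance is (0.111 + 0.778 + 0.778)/3 = 0.556. The very small pre residual pulls down the variance applied at post. Simulation gave ungated error of 9.2, 9.8 and 10.2%.

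These figures concern the difference between arms at post-training, which is how the SAP words its contrasts. Change from pre is different. A participant-level covariate cancels from within-person change when data are complete, so the interaction test is the same with or without it, except when the random-intercept variance is estimated at zero. In simulation the interaction decision differed from the unadjusted one in at most 0.3% of trials (0.8% at 30 per arm).

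The gate also matters. With no arm differences, gated error for MA-MBSR versus MO-MBSR was 1.9 to 2.0%. With both arms an assumed 0.6 SD better than CC and equal to each other, the gate usually opens, and error was 8.2 to 10.3%, against 4.2 to 5.2% in the unadjusted model.

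**ARH(1) fitted to the same model.** ARH(1) gives each occasion its own variance. A slope of 1 with zero pre intercepts fits the pre row exactly, so the pre SD can shrink without limit. The REML log-likelihood then behaves as −(N − 4) ln(pre SD), where 4 counts the three arm means at pre and the slope. Each tenfold fall in pre SD lowers −2 log L by 2 × 176 × ln 10 = 811. On one simulated data set, with the pre SD fixed at 0.135, 0.018, 0.0025 and 0.0003, −2 log L was 582, −125, −829 and −1533, against 1209 for compound symmetry. There is no maximum, so an AIC comparison involving this fit means nothing.

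**MCAR sentence.** The SAP's MLMs use all available outcomes. REML is stated for the EMA models, and a likelihood-based fit is implied for the symptom model. Such a model is valid when dropout depends on arm and observed outcomes, provided its mean and covariance models are adequate. The pre score is already an observed response, so entering it again as a covariate relaxes nothing. Covariates that are not responses (age, sex, gender, race, subtype) do extend MAR to dropout that depends on them.

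As an illustration, a simulation assumed 80 per arm, r = 0.5, no true effect, and about 15% dropout depending on baseline in opposite directions by arm. For the arm-by-occasion effect at post:
- unadjusted model: bias 0.004 SD, error 4.9%;
- pre score as both response and covariate: bias 0.095 SD, error 10.4%;
- pre score as covariate only: bias −0.001 SD, error 4.8%.

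That mechanism is deliberately strong. When dropout depended on baseline in one arm only, the double-use model had bias 0.024 SD and error 6.3%.

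**The case against.** The strongest reply is that the faulty model is inferred from silence. The symptom equation is given without covariates, the adjusted models have no equation, and the covariates form one generic list for several outcomes. For many of those outcomes baseline severity and baseline perceived stress are proper covariates. This stands as a limit. The problem arises only where covariate and outcome are the same measure and the pre row is kept. An IBS-SS covariate does no such harm in a model of clinician- or physician-assessed symptoms, and momentary EMA scores are not affected in this way. It does not remove the point, because the general model has pre as a response and the covariate list makes no exception.

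A reader might infer that the trial's main conclusion is at risk. The documents do not support that: the decision rests on the unadjusted interaction, which this does not touch, and the adjusted interaction is nearly the same with complete data.

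A reader might also infer that the AIC step would cost power or distort error by a stated amount. The SAP says only that other structures will be evaluated. It does not say that the lowest AIC wins mechanically or that the structure is chosen again for each adjusted fit. Any figure would depend on where software bounds the pre variance, and a competent analyst would probably see that the fit is degenerate. No power or error figure belongs to that fit.

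Finally, a reader might say that the SAP calls its own primary analysis invalid, or that this analysis is biased by dropout. Neither follows. The sentence on expected dropout describes MAR, of which MCAR is a special case, so the two statements can both be true. Bias calculated for participants with complete outcomes does not apply to a model of all available data. The SAP also plans pattern-mixture sensitivity analyses.

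**Conclusion.** The point holds in limited form and is minor.

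- **Double use of the pre score.** The SAP leaves it open, and a plain reading for the self-reported symptom model leads to it if baseline severity is the IBS-SS. Under compound symmetry the affected post-training contrasts have standard errors about 14 to 17% too small and ungated error of about 9 to 10%. This rests on assumed r = 0.3 to 0.7, equal variances and complete data. With ARH(1), the model has no maximum likelihood.
- **MCAR statement.** It is wrong as written, whichever instruments are used. The correct condition is MAR given arm and observed outcomes, with adequate mean and covariance models.

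The primary unadjusted test stands. What needs repair is a sensitivity analysis and the description of a missing-data assumption.

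**What to change.** Name the instrument behind each baseline covariate. Then state for each outcome which of two forms the adjusted model takes:

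- **(a)** Keep the pre score as a response, leave that same value out of the covariates, and keep the occasion-by-treatment interaction as the test.
- **(b)** Use the pre score as a covariate, with a baseline-by-occasion term, and keep only post and follow-up as responses. The tested effect must then change to the arm effects at post and follow-up, tested jointly and followed by the planned contrasts. With the pre row gone, the occasion-by-treatment interaction would ask only whether arm effects differ between post and follow-up, and would miss a benefit that is equal at both.

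Replace the MCAR sentence with: *The unadjusted likelihood-based models are valid under MAR given observed outcomes and treatment arm, provided the mean and covariance models are adequate; the adjusted models extend this to dropout that depends on the added covariates.*

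The cost is SAP wording and a small change to a sensitivity analysis. No new data are needed and the primary test does not change.
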